7.3. Determination of Sample Size

Up to 60 healthy subjects may be enrolled to ensure that at least 40 subjects complete the study. With 40 subjects completing, there is 80% coverage probability that the half-width of the 90% confidence interval (CI) of the difference of means for AUC will be within 0.223 in the log scale, which corresponds to approximately 20% in the ratio scale. This precision estimate was based on the intrasubject variability for AUC of 39.26% observed in completed studies in healthy

subjects. Drop-outs may be replaced and the replacement subject would assume the withdrawn subject's treatment sequence (receiving both allocated treatments).

8. Study Population

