Protocol I4L-MC-ABEF(c)

Relative Bioavailability of LY2963016 to LANTUS® After Single-Dose Subcutaneous Administration in Healthy Chinese Subjects

NCT03555305

Approval Date: 18-Dec-2018

1. Protocol I4L-MC-ABEF(c)

**Relative Bioavailability of LY2963016 to LANTUS® after
Single-Dose Subcutaneous Administration in Healthy
Chinese Subjects**

Confidential Information

The information contained in this protocol is confidential and is intended for the use of clinical investigators. It is the property of Eli Lilly and Company or its subsidiaries and should not be copied by or distributed to persons not involved in the clinical investigation of LY2963016, unless such persons are bound by a confidentiality agreement with Eli Lilly and Company or its subsidiaries. This document and its associated attachments are subject to US Freedom of Information Act (FOIA) Exemption 4.

LY2963016

This is a randomised, open-label, single-dose (0.5 U/kg), 2-treatment, 2-period, crossover study to compare the bioavailability of LY2963016 relative to that of LANTUS®.

Eli Lilly and Company
[name]

Protocol Electronically Signed and Approved by Lilly: 15 April 2013
Amendment (a) Electronically Signed and Approved by Lilly: 24 May 2017
Amendment (b) Electronically Signed and Approved by Lilly: 14 June 2018
Protocol Amendment (c) Electronically Signed and Approved by Lilly on date provided below.

Approval Date: 18-Dec-2018 GMT

2. Synopsis

Clinical Pharmacology Protocol Synopsis: Study I4L-MC-ABEF

Name of Investigational Product: LY2963016	
Title of Study: Relative Bioavailability of LY2963016 to LANTUS® after Single-Dose Subcutaneous Administration in Healthy Chinese Subjects	
Number of Planned Subjects: Up to 60 subjects may be enrolled in order for 40 subjects to complete the study.	Phase of Development: 1
Length of Study: Approximately 1 month	
Objectives:	

Primary: To evaluate the relative bioavailability of LY2963016 compared to LANTUS following subcutaneous (SC) single-dose administrations (0.5 U/kg) in healthy Chinese subjects.
	
Secondary Objectives:	

 • To evaluate safety and tolerability of LY2963016 when administered to healthy Chinese subjects. • To compare other pharmacokinetic (PK) parameters of LY2963016 with those of LANTUS after 0.5-U/kg SC administration. • To compare the pharmacodynamic (PD) responses of LY2963016 with those of LANTUS after 0.5-U/kg SC administration. 	

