3. INTRODUCTION

This SAP has been developed after review of the Clinical Study Protocol (final version dated 15 April 2013) and Protocol Amendment (a) (final version dated 24 May 2017).

The SAP is being updated from Version 1 to Version 2 due to errors in the protocol and include updates to Section 7, Section 9.3.2 and Section 9.4.2.

This SAP describes the planned analysis of the safety, tolerability, pharmacokinetic (PK) and pharmacodynamic (PD) data from this study. A detailed description of the planned TFLs to be presented in the clinical study report (CSR) is provided in the accompanying TFL shell document.

The intent of this document is to provide guidance for the statistical and PK analyses of data. In general, the analyses are based on information from the protocol, unless they have been modified by agreement between Eli Lilly and Company and Covance Early Clinical (EC) Biometrics. A limited amount of information concerning this study (e.g., objectives, study design) is given to help the reader's interpretation. This SAP must be signed off prior to first subject administration for this study. When the SAP and TFL shells are agreed upon and finalized, they will serve as the template for this study's CSR.

This SAP supersedes the statistical considerations identified in the protocol; where considerations are substantially different, they will be so identified. If additional analyses are required to supplement the planned analyses described in this SAP, they may be performed and will be identified in the CSR. Any substantial deviations from this SAP will be agreed upon between Eli Lilly and Company and Covance EC Biometrics and identified in the CSR. Any minor deviations from the TFLs may not be documented in the CSR.

This SAP is written with consideration of the recommendations outlined in the International Council on Harmonisation (ICH) E9 Guideline entitled Guidance for Industry: Statistical Principles for Clinical Trials¹ and the ICH E3 Guideline entitled Guidance for Industry: Structure and Content of Clinical Study Reports².

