5. STUDY DESIGN

This is a randomised, open-label, single-dose (0.5 U/kg), 2-treatment, 2-period, crossover, single-site, euglycaemic clamp study to evaluate the relative bioavailability of LY2963016 to LANTUS in healthy subjects. The study will have 2 treatment periods, with subjects randomly assigned in a 1:1 fashion to a treatment sequence of either LY2963016 (Period 1) followed by LANTUS (Period 2), or LANTUS (Period 1) followed by LY2963016 (Period 2) (Figure 1). Study drug will be administered once per period as an SC dose. Up to 60 healthy men and women will be enrolled in order to ensure that 40 subjects complete the study.

[figure not shown]

Figure 1. Study design

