7. SAMPLE SIZE JUSTIFICATION

Up to 60 healthy subjects may be enrolled to ensure that at least 52 subjects complete the study. Assuming the ratio of AUC between test and reference product is 1, with 52 subjects completing, there is 80% coverage probability that the half-width of the 90% confidence interval (CI) of the difference of means for the area under the concentration time curve (AUC) will be within 0.223 in the log scale, which corresponds to approximately 20% in the ratio scale. This precision estimate was based on the intrasubject variability for AUC of 39.26% observed in completed studies in healthy subjects. Drop-outs may be replaced and the replacement subject would assume the withdrawn subject's treatment sequence (receiving both allocated treatments).

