11. CHANGES FROM THE PROTOCOL SPECIFIED STATISTICAL ANALYSES

There were no changes from the protocol specified statistical analyses.

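### One 80% precision statement supports 40 completers in Protocol 7.3 and 52 in SAP 7; the other sections still say 40, and 80% is not the probability described at 40 on any of three readings of the variability figure

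*Protocol*

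**What the plan says.** Protocol 7.3 asks for at least 40 completers from up to 60 enrolled and justifies this by precision: "With 40 subjects completing, there is 80% coverage probability that the half-width of the 90% confidence interval (CI) of the difference of means" for AUC does not exceed 0.223 on the log scale, described as about 20% on the ratio scale. The input is an intrasubject variability of 39.26%, which is not labelled as a CV, an SD or a variance.

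SAP 7 asks for at least 52 completers from the same cap of 60: "Assuming the ratio of AUC between test and reference product is 1, with 52 subjects completing, there is 80% coverage probability", followed by the same half-width limit and the same 39.26%. The only new input is the assumed true ratio of 1.

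The other statements of the target were not changed. The Protocol Synopsis has "Up to 60 subjects may be enrolled in order for 40 subjects to complete the study", and SAP 5 has "Up to 60 healthy men and women will be enrolled in order to ensure that 40 subjects complete the study", as does Protocol 7.1.

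SAP 3 explains that the SAP was "updated from Version 1 to Version 2 due to errors in the protocol and include updates to Section 7" (and to 9.3.2 and 9.4.2), and adds: "This SAP supersedes the statistical considerations identified in the protocol; where considerations are substantially different, they will be so identified". It does not say what the error in the sample-size section was. SAP 11 reads: "There were no changes from the protocol specified statistical analyses".

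**The concern.** Two things look wrong.

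First, the target is inconsistent. Five places state the number of completers: four say 40 and one says 52. One of the four is in the SAP, so the clause giving the SAP precedence over the Protocol does not settle it.

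Second, the justification does not identify its own calculation. With the confidence level, half-width limit and variability all fixed, the probability depends only on the number of completers. The same 80% cannot belong to both 40 and 52. The assumption that SAP 7 adds, a true ratio of 1, does not enter a half-width probability at all, because the width of the interval does not depend on where it is centred.

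At stake is when enrolment and the optional replacement of drop-outs can be treated as finished, and what assurance the study was planned to give for the primary AUC comparison. Under the cap of 60, a target of 40 allows 60 − 40 = 20 losses (33%); a target of 52 allows 60 − 52 = 8 (13%).

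**Working it through.** **Inputs.** N = 40 (Protocol 7.3) or 52 (SAP 7); limit 0.223; 90% two-sided CI; variability 39.26% (both sections). Two-sequence, two-period crossover with 1:1 allocation (Protocol 7.1) and the mixed model of Protocol 12.1.4.2, so residual df = N − 2.

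**The limit itself reproduces.** exp(−0.223) = 0.800 and exp(0.223) = 1.250, so 0.223 is ln 1.25 to three decimals.

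**Three readings of 39.26%.**
- CV: log SD = √ln(1 + 0.3926²) = 0.3786
- log SD: 0.3926
- log variance: log SD = √0.3926 = 0.6266

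**Probability as worded.** The half-width is t(0.95, N−2) × s × √(2/N), where s is the estimated within-subject log SD. Write H for its value when s equals the true SD. Then

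P(half-width ≤ 0.223) = P(χ² with N−2 df ≤ (N−2) × (0.223/H)²).

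- CV reading, N = 40: SE = 0.3786 × √(2/40) = 0.0847; t = 1.686; H = 0.143; χ² bound 92.8 on 38 df; P = 0.999998.
- CV reading, N = 52: SE = 0.0743; t = 1.676; H = 0.124; χ² bound 160.6 on 50 df; P = 1 to more than ten decimals.
- Log-variance reading, N = 40: H = 0.236; χ² bound 33.9 on 38 df; P = 0.339.
- Log-variance reading, N = 52: H = 0.206; χ² bound 58.6 on 50 df; P = 0.812.

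| Reading | N = 40 | N = 52 | Smallest N reaching 80% |
|---|---|---|---|
| CV | >99.9% | >99.9% | 22 (82.3%) |
| log SD | >99.9% | >99.9% | 23 (80.5%) |
| log variance | 33.9% | 81.2% | 52 (51 gives 78.0%) |

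The stated 80% is therefore not reproduced at 40 on any reading. At 52 it is reproduced only if 39.26% is a log-scale variance. Working backwards, 80% would need a log SD of about 0.543 at 40 and about 0.629 at 52.

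**Half-width that does carry 80% assurance.** CV reading: about 0.155 at 40 and 0.134 at 52. Log-SD reading: about 0.161 and 0.139.

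**What may have been calculated (inference; neither document says so).** A true ratio of 1 and a limit of ln 1.25 are the inputs for the probability that the whole 90% CI lies within 0.80 to 1.25. Integrating over the χ² distribution of s², at true ratio 1:

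| Reading | N = 40 | N = 50 | N = 52 | N = 56 |
|---|---|---|---|---|
| CV | 65.5% | 79.2% | 81.3% | – |
| log SD | 60.5% | – | 77.5% | 81.5% |

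A simulation on the CV reading agrees with the integration (about 66% at 40, 81% at 52). On that reading 52 is the smallest even N reaching 80%. The 40 matches a different quantity: power of a single one-sided 5% test against a difference of 0.223 with log SD 0.3926, which is 79.3% at 39 and 80.2% at 40 (82.7% at 40 on the CV reading).

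**The case against.** The best defence is that the SAP has already dealt with this. It says that it supersedes the Protocol's statistical considerations and that its Section 7 was updated because the Protocol was in error, so 52 is the disclosed correction and SAP 5 is merely out of date. That probably describes the intent. It does not repair SAP 5, it leaves the Protocol under which the site enrols at 40, and it does not say what the error was.

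A second defence is that SAP 7 has not been shown to be wrong. If 39.26% is a log variance, its sentence is correct and 52 is the smallest number that satisfies it. On the other two readings the stated precision is exceeded at both sizes, so the property as written has no shortfall. Both points stand. They mean that SAP 7 is ambiguous, not demonstrably false; they do not rescue 80% at 40.

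Third, the 65% figure uses limits found in neither document, and the two proposed origins need different readings of one number (CV for 52, log SD for 40). This stands too: the origins are conjecture, and the figure is conditional on them.

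Fourth, the targets are floors, replacement is optional, and 52 completers satisfy every section. Nothing requires stopping at 40. That limits the consequence. Lastly, SAP 11 speaks of analyses, and a completer target is arguably not one; SAP 3 promises that differences will be identified but does not name SAP 11 as the place. The promise is nevertheless not kept anywhere else in the SAP for this number.

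**Conclusion.** The concern holds. The completer target is 40 in four places and 52 in one, with a conflict inside the SAP itself. The 80% attached to 40 is wrong on the CV, log-SD and log-variance readings (above 99.9%, above 99.9% and 34%). The 80% attached to 52 is right only on the log-variance reading (81%). These figures rest on the standard two-period crossover with N − 2 df and balanced sequences.

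The effect on the planned assurance depends on which property was meant. For the half-width as written, on the CV or log-SD reading, both sizes are more than sufficient. For containment of the 90% CI in 0.80 to 1.25 at a true ratio of 1 (assumed limits), finishing with 40 rather than 52 lowers the probability from 81% to 65% on the CV reading, and from 78% to 61% on the log-SD reading. The planned estimates, intervals and error rates are unaffected.

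**What to change.** 1. State one completer number in the Protocol Synopsis, Protocol 7.1 and 7.3, SAP 5 and SAP 7. The SAP's own correction, 52, fits within the cap of 60.
2. Say whether 39.26% is a within-subject CV, a log-scale SD or a log-scale variance.
3. Replace the half-width sentence with the property actually calculated, naming any limits. If that was containment of the CI and 39.26% is a CV, the text could read: *Assuming a true AUC ratio of 1 and a within-subject CV of 39.26%, 52 completers give about 81% probability that the 90% CI for the ratio lies within 0.80 to 1.25.* If half-width precision was meant and 39.26% is a log variance, keep the sentence with 52, add that label and drop the assumed ratio.
4. If 40 is kept, restate its figure. On the CV reading this is an 80%-assured half-width of about 0.155, or about 65% for containment.
5. Record in the SAP, most naturally in SAP 11, what was corrected relative to Protocol 7.3 and why.

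The cost is wording in both documents. Protocol 10.5 sends major modifications to an amendment, so changing the number in the Protocol may need one. The cap does not change, but a target of 52 leaves room for 8 losses instead of 20.

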8.1. Criteria for Enrolment

Eligibility of subjects for study enrolment will be based on the results of a screening medical history, physical examination, clinical laboratory tests, and ECG. The nature of any conditions present at the time of the physical examination and any preexisting conditions will be documented.

Screening may occur up to 4 weeks prior to enrolment.

Individuals who do not meet the criteria for participation in this study (screen failure) may be re-screened. Individuals may be re-screened once. The interval between re-screenings should be at least 2 weeks. If re-screening is performed, the individual must sign a new informed consent form (ICF) and will be assigned a new identification number.

Prospective approval of protocol deviations to recruitment and enrolment criteria, also known as protocol waivers or exemptions, are not permitted.

8.1.1. Inclusion Criteria

Subjects are eligible for enrolment in the study only if they meet **all** of the following criteria:

- [1] Are native Chinese men or women. Native Chinese is defined as a subject who has both parents and all 4 grandparents of Chinese origin.
- [2] Are overtly healthy males or females, as determined by medical history and physical examination.
- [3a] For females of childbearing potential (defined as not surgically sterilised and between menarche and 1-year postmenopause) only:
 - Negative serum pregnancy test at the time of screening.
 - Are not lactating.
 - Intend not to become pregnant during the study.
 - Are sexually inactive or have practiced a reliable method of birth control (for example, use of oral contraceptives or levonorgestrel; diaphragms with contraceptive jelly; cervical caps with contraceptive jelly; condoms with contraceptive foam; intrauterine devices; partner with vasectomy; or abstinence) for at least 6 weeks prior to screening.
 - Agree to continue to use a reliable method of birth control (as determined by the investigator) during the study.
- [3b] For females not of childbearing potential, must be:
 - Surgically sterile, defined as having had a hysterectomy or bilateral oophorectomy or tubal ligation, and/or

- Menopausal, defined as having had no menses for at least 1 year, or a plasma follicular stimulating hormone value of >40 mIU/mL and no menses for at least 6 months, unless the subject is taking hormone-replacement therapy.

[4] Are between the ages of 18 and 40 years, inclusive, at screening.

[5] Having fasting plasma glucose <110 mg/dL (<6.1 mmol/L) and 2-hour glucose level <140 mg/dL (<7.8 mmol/L) on the 75 g oral glucose tolerance test.

[6] Have a body mass index (BMI) between 18 and 28 kg/m², inclusive, at screening.

[7] Are nonsmokers, have not smoked for at least 6 months prior to entering the study, and agree not to smoke (cigars, cigarettes, or pipes) or use smokeless tobacco for the duration of the study.

[8] Have normal blood pressure and pulse rate at screening, as determined by the investigator.

[9] Have an ECG, at screening, considered as within normal limits by the investigator.

[10] Have clinical laboratory test results within normal reference range for the population or investigator site, or results with acceptable deviations that are judged to be not clinically significant by the investigator.

[11] Have venous access sufficient to allow for blood sampling as per the protocol.

[12] Are reliable and willing to make themselves available for the duration of the study and are willing to follow study procedures.

[13] Have given written informed consent approved by Lilly and the ethical review board (ERB) governing the site.

8.1.2. Exclusion Criteria

Subjects will be excluded from study enrolment if they meet **any** of the following criteria:

[14] Are investigator site personnel directly affiliated with this study and their immediate families. Immediate family is defined as a spouse, parent, child, or sibling, whether biological or legally adopted.

[15] Are Lilly or Boehringer Ingelheim employees.

[16] Have a history of first-degree relatives known to have diabetes mellitus.

[17] Are persons who have previously completed or withdrawn from this study.

[18] Are currently enrolled in, have completed or discontinued within the last 30 days from a clinical trial involving an investigational product; or are concurrently enrolled in any other type of medical research judged not to be scientifically or medically compatible with this study.

- [19] Have known allergies to insulin glargine or its excipients, or related drugs, or heparin, or have a history of relevant allergic reactions of any origin.
- [20] Have a significant history of or current cardiovascular, respiratory, hepatic, renal, gastrointestinal, endocrine, haematological, or neurological disorders capable of significantly altering the absorption, metabolism, or elimination of drugs; of constituting a risk when taking the study medication; or of interfering with the interpretation of data.
- [21] Show evidence of current significant active neuropsychiatric disease.
- [22] Show evidence of current use of known drugs of abuse or a history of use within the past year.
- [23] Show evidence of human immunodeficiency virus infection (HIV) and/or positive human HIV antibodies.
- [24] Have positive hepatitis B surface antigen.
- [25] Have donated >400 mL of blood in the last 6 months or donated >100 mL within the last 30 days.
- [26] Have an average weekly alcohol intake that exceeds 21 units per week (males) and 14 units per week (females), or are unwilling to stop alcohol consumption while resident in the CRU (1 unit = 12 ounces or 360 mL of beer; 5 ounces or 150 mL of wine; 1.5 ounces or 45 mL of distilled spirits).
- [27] Intend to use: prescription medication or over-the-counter medication or Chinese traditional medicine within 14 days before dosing (apart from vitamin/mineral supplements, occasional paracetamol, thyroid replacement, or birth control methods). If this situation arises, an otherwise suitable subject may be included at the discretion of the investigator.
- [28] Are persons determined by the investigator to be unsuitable for any other reason.

8.2. Discontinuation

8.2.1. Discontinuation of Subjects

If the Sponsor or investigator identifies a subject who did not meet enrolment criteria and was inadvertently enrolled, a discussion must occur between the Lilly clinical pharmacologist/clinical research physician and the investigator to determine if the subject may continue in the study. If both agree it is medically appropriate to continue, the investigator must obtain documented approval from the Lilly clinical pharmacologist/clinical research physician to allow the inadvertently enrolled subject to continue in the study with or without continued treatment with investigational product.

Some possible reasons for early discontinuation of study participation:

- Enrolment in any other clinical trial involving an investigational product or enrolment in any other type of medical research judged not to be scientifically or medically compatible with this study.
- Investigator/Physician Decision
 - the investigator/physician decides that the subject should be withdrawn from the study
- Subject Decision
 - the subject requests to be withdrawn from the study
- Sponsor Decision
 - the investigator or Lilly stops the study or stops the subject's participation in the study for medical, safety, regulatory, or other reasons consistent with applicable laws, regulations, and GCP
- Adverse Event
 - if a clinically significant event (CSE) occurs, the investigational product is to be discontinued and appropriate measures taken. Lilly or its designee should be alerted immediately. A CSE will be defined as a moderate to severe AE, abnormal clinical sign, or clinical laboratory finding that may pose a risk to the well-being of the subject. Refer to Section 10.3.

The nature of any conditions, clinical signs or symptoms, or abnormal laboratory values present at the time of discontinuation and any applicable follow-up procedures will be documented.

Discontinuation procedures are outlined in the Study Schedule ([Attachment 1](#)).

8.2.2. Discontinuation of Study Sites

Study site participation may be discontinued if Lilly, the investigator, or the ERB of the study site judges it necessary for any reason consistent with applicable laws, regulations, and GCP.

